9.4.2 ANALYSIS OF THE PRIMARY OUTCOMES

See above 9.4.1

9.4.3 ANALYSIS OF THE EXPLORATORY OUTCOMES

See above 9.4.1

9.4.4 SAFETY ANALYSES

Safety outcome will be the adverse effects questionnaire filled out at the end of each stimulation session (mean, median, and range), and the presence of AEs, SAEs, and UAEs which are deemed to be related to stimulation. AEs, SAEs, and UAEs reporting will be done at each stimulation visit, as well as 1 day and 4 days after each visit over telephone. Each AE will be counted only once per participant. AEs will be reported as start date, stop date, severity, relationship to stimulation, expectedness, outcome, and duration. Adverse events leading to premature discontinuation from the study, and serious treatment-emergent AEs, will be presented in a table.

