4 STUDY DESIGN

4.1 OVERALL DESIGN

This is a prospective, triple crossover (three stimulation sites which will be done at separate study visits), single-blinded study design. The difference in stimulation site precludes double-blinding as the study personnel will be aware of the difference in location while running the experiment.

Aim 1: To determine whether iTBS to the medial prefrontal cortex (mPFC) produces more robust changes in frontal midline theta (FMT) EEG power in people with Parkinson's disease compared with stimulation at the dorsolateral prefrontal cortex (DLPFC) or the primary sensory cortex (S1).

Hypothesis:

H_0 : Mean change in Frontal midline theta power on electroencephalogram after iTBS to the medial prefrontal cortex will be equal to FMT changes after dorsolateral prefrontal cortex stimulation and stimulation of S1.

H_1 : Mean change in Frontal midline theta power on electroencephalogram after iTBS to the medial prefrontal cortex will be greater than FMT changes after dorsolateral prefrontal cortex stimulation and stimulation of S1.

Aim 2A: To identify associations between symptoms of autonomic dysfunction at baseline before stimulation and frontal midline theta band frequency on electroencephalogram.

H_0 : There is zero correlation between severity of autonomic dysfunction symptoms at baseline before stimulation with frontal midline theta power at baseline on electroencephalogram.

H_1 : There is a negative correlation between severity of autonomic dysfunction symptoms at baseline before stimulation with frontal midline theta power at baseline on electroencephalogram.

Aim 2B: To identify associations between symptoms of depression at baseline before stimulation and frontal midline theta band frequency on electroencephalogram.

Hypothesis:

H_0 : There is no correlation between severity of depression symptoms at baseline before stimulation with frontal midline theta power on electroencephalogram at baseline.

H_1 : There is negative correlation between depression symptoms at baseline before stimulation with frontal midline theta power on electroencephalogram at baseline.

Exploratory objectives

Aim 3: To evaluate the effect of iTBS on autonomic symptoms one day after, and 4 days after stimulation.

Hypothesis:

H_0 : Change in SCOPA-AUT and OHQ will be zero one day after stimulation and 4 days after stimulation compared to pre-stimulation.

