8.3.3.2 RELATIONSHIP TO STUDY INTERVENTION

All adverse events (AEs) must have their relationship to study intervention assessed by the clinician who examines and evaluates the participant based on temporal relationship and his/her clinical judgment. The degree of certainty about causality will be graded using the categories below. In a clinical trial, the study product must always be suspect.

- **Related** – The AE is known to occur with the study intervention, there is a reasonable possibility that the study intervention caused the AE, or there is a temporal relationship between the study intervention and event. Reasonable possibility means that there is evidence to suggest a causal relationship between the study intervention and the AE.
- **Not Related** – There is not a reasonable possibility that the administration of the study intervention caused the event, there is no temporal relationship between the study intervention and event onset, or an alternate etiology has been established.

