8.3.4 TIME PERIOD AND FREQUENCY FOR EVENT ASSESSMENT AND FOLLOW-UP

The occurrence of an adverse event (AE) or serious adverse event (SAE) may come to the attention of study personnel during study visits, during study telephone calls, and interviews of a study participant presenting for medical care.

All AEs including local and systemic reactions not meeting the criteria for SAEs will be captured on the appropriate case report form (CRF). Information to be collected includes event description, time of onset, clinician's assessment of severity, relationship to study product (assessed only by those with the training and authority to make a diagnosis), and time of resolution/stabilization of the event. All AEs occurring while on study must be documented appropriately regardless of relationship. All AEs will be followed to adequate resolution.

Any medical condition that is present at the time that the participant is screened will be considered as baseline and not reported as an AE. However, if the study participant's condition deteriorates at any time during the study, it will be recorded as an AE.

Changes in the severity of an AE will be documented to allow an assessment of the duration of the event at each level of severity to be performed. AEs characterized as intermittent require documentation of onset and duration of each episode.

Study personnel will record all reportable events with start dates occurring any time after informed consent is obtained until 7 (for non-serious AEs) or 30 days (for SAEs) after the last day of study participation. At each study visit, the investigator will inquire about the occurrence of AE/SAEs since the last visit. Events will be followed for outcome information until resolution or stabilization.

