8.3.5 ADVERSE EVENT REPORTING

All AEs will be captured and recorded at each stimulation visit in person, and one day after, and four days after each stimulation visit over telephone. The AE report form will be completed by the researcher, and will include details about the stimulation, what is known about previous reported side effects, if the AE occurred in temporal relation to the stimulation, whether the AE improves or completely resolves once stimulation is ceased, whether the AE is worsening of a baseline symptom, and whether the AE is related to concurrent medication or medical condition. This form will be presented to the PI who will review and sign the form. Completed forms will be placed in the participant's file in the study binder. AEs will also be documented in the AE log, which will also document the date, severity, relationship to treatment (as determined by the PI), actions taken, and outcome. Medical conditions and symptoms present prior to start of stimulation on the day of the visit will not be considered an AE.

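### The AE part of the safety outcome counts only events deemed related to stimulation, but the Related and Not Related definitions overlap and no rule says which prevails

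*Combined protocol and SAP*

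**What the plan says.** Section 9.4.4 gives the safety outcome two parts. The first is unfiltered: "Safety outcome will be the adverse effects questionnaire filled out at the end of each stimulation session (mean, median, and range"). The second is filtered on causality: "the presence of AEs, SAEs, and UAEs which are deemed to be related to stimulation". The same section says AEs will be reported with several attributes, relationship to stimulation among them. It also promises a table of AEs leading to premature discontinuation and of serious treatment-emergent AEs.

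Section 8.3.3.2 defines the filter. Related covers an event that is known to occur with the intervention, or where "there is a reasonable possibility that the study intervention caused the AE, or there is a temporal relationship between the study intervention and event". Not Related covers an event with no reasonable possibility of causation, or where "there is no temporal relationship between the study intervention and event onset, or an alternate etiology has been established". The section adds a general statement that the study product is to be regarded with suspicion. It assigns the assessment to the clinician who examines the participant.

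On collection, 8.3.4 says "All AEs occurring while on study must be documented appropriately regardless of relationship". In 8.3.5 the AE log holds the "relationship to treatment (as determined by the PI"). On masking, 4.1 states that "the study personnel will be aware of the difference in location while running the experiment"; 6.2 blinds participants only.

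**The concern.** A filter on an outcome should give one answer per event, and this one can give two. Temporal relationship alone is enough for Related, and an established alternate etiology alone is enough for Not Related. The plan does not say what to do when both hold.

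The filter is also a judgement. It is made in a trial where study personnel know the stimulation site, the AE form that the PI reviews includes details of the stimulation (8.3.5), and safety oversight rests with the PI and advisors (10.1.7). No masked or independent causality review is described.

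What is at stake is the reported count of ordinary AEs. Two careful assessors following the plan could classify the same event differently, and one of them would leave it out of the safety outcome. The judgement is avoidable, because the data for an all-cause count are already collected.

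**Working it through.** The plan gives no figure to reproduce here, so the check is on the logic of the two definitions.

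**Inputs, all from 8.3.3.2.** Describe an event by four yes/no attributes:
- K: known to occur with the intervention
- R: reasonable possibility that the intervention caused it
- T: temporal relationship
- A: alternate etiology established

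This gives 2 × 2 × 2 × 2 = 16 combinations.

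**Related** = K or R or T. It fails only when K, R and T are all no, which is 2 combinations (A yes or no). So 16 − 2 = 14 combinations are Related.

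**Not Related, literal reading** (any listed condition suffices) = not R, or not T, or A. It fails only when R and T are yes and A is no, which is 2 combinations (K yes or no). So 16 − 2 = 14 are Not Related. No combination falls in neither category, so the overlap is 14 + 14 − 16 = 12 of 16.

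**Not Related, narrower reading** (the first two conditions must hold together) = (not R and not T), or A. It holds in the 8 combinations with A yes, plus 2 with A, R and T all no, making 10. Again none falls in neither category, so the overlap is 14 + 10 − 16 = 8 of 16.

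These are counts of logical combinations, not of events, and some combinations will be rarer than others. They show only that the overlap survives the more charitable reading.

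**Particular cases**

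| Event | Literal reading | Narrower reading |
|---|---|---|
| T yes, A yes (for example, headache soon after a session with an established other cause) | Both | Both |
| K yes, T no, A no (for example, a headache, listed as a risk in 2.3.1, without temporal relationship) | Both | Both only if R is also no |
| T yes, R no, A no | Both | Related only |

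**Which reports are exposed**
- Questionnaire: no relatedness filter, but completed at the end of the session, so it does not capture events first reported at the day 1 or day 4 call.
- Serious treatment-emergent AEs and AEs leading to discontinuation: tabulated without a relatedness filter (9.4.4).
- Other non-serious AEs: no separate table is promised, so they depend on the filter.

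**Effect on the count.** Among the exposed AEs, let r be those that meet only Related, n those that meet only Not Related, and b those that meet both. The reported number then lies between r and r + b, out of r + n + b recorded. The uncertainty is b. The documents give no AE counts or rates, so b cannot be computed.

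**The case against.** The case for leaving the text alone has several parts.

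*Relationship is already a reported attribute.* Listing relationship for each AE in 9.4.4 makes most sense if unrelated AEs are reported too. This has force, but the sentence defining the outcome still restricts it to related events, and nothing says that the attribute sentence covers the rest. Section 9.4.8 rules out individual listings. The two sentences of 9.4.4 need to be made to agree.

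*The plan leans towards Related.* Section 8.3.3.2 says to keep the product under suspicion, and an alternate etiology must be established, not merely available. Both narrow the overlap in practice. Neither says what happens once another cause is established for an event close to stimulation.

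*Parkinson's symptoms do not create the overlap by themselves.* A reader might infer that dizziness after a session, in a participant with orthostatic hypotension, automatically meets both definitions. The documents do not support that. Symptoms present before stimulation that day are not AEs (8.3.5), and conditions present at screening count only if they deteriorate (8.3.4). A known condition is also not yet an established cause of a new or worse event. This objection stands.

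*Site knowledge has no planned contrast to distort.* A reader might infer bias in a safety comparison between sites. Section 9.4.4 plans no such comparison, and 4.1 speaks of personnel while running the experiment, not of the causality assessor for each event. This stands too. What remains is that the judgement is discretionary and has no described masking.

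*Clinician and PI may be successive steps.* The clinician may assess and the PI may then review and record. That is a fair reading, so this is a point to clarify and not a firm contradiction.

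**Conclusion.** The concern holds in a limited form. The AE part of the safety outcome is filtered on a classification whose two categories overlap (12 of 16 attribute combinations on the literal reading, 8 of 16 on the narrower one), with no precedence rule. The consequence is an ill-defined count of non-serious AEs that do not lead to discontinuation, in the descriptive safety reporting of a pilot study. It does not touch the EEG outcomes.

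The size cannot be derived from the documents. A reader might take the statement in 2.2 that autonomic dysfunction affects more than half of patients as the share of AEs open to either classification. It is a prevalence of symptoms in the disease, not a share of AEs, and the documents offer no other basis for a figure. Nor could the reported count range up to all recorded AEs, since events that are plainly Not Related stay out under any reading. A reader might also infer that events are lost from the trial. They are not: they are recorded whatever their relationship and reviewed at least quarterly (9.4.6).

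The conclusion rests on taking the outcome sentence in 9.4.4 as written. If the sponsor intends to report all AEs, the change below only states that intention.

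**What to change.** 1. In 9.4.4, define the AE part of the safety outcome as all AEs, SAEs and UAEs starting after the first stimulation, regardless of causality, with related events reported as a subset. The start point must be stated because 8.3.4 collects events from consent onwards. The main count then no longer depends on the causality judgement.
2. In 8.3.3.2, make the two categories mutually exclusive and state which prevails. One workable form is to call an event Not Related only when there is no reasonable possibility of a causal role, and Related otherwise.
3. Reconcile 8.3.3.2 and 8.3.5 on whose determination is final. If the clinician assesses and the PI confirms, say so.

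The cost is wording in three sections, with no new data and no extra visits. The downside is that reported AE counts will be somewhat higher, because events judged unrelated will appear.

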1 PROTOCOL SUMMARY

1.1 SYNOPSIS

Title:	Investigating Central Neurophysiologic Correlates of Non-motor Symptoms of Parkinson's Disease
Study Description:	This is a randomized, single-blinded, triple crossover study with 3 one-day iTBS, separated by a wash-out period of 3 weeks ¹ , sufficient for physiologic effects of one session of iTBS to return to baseline. Participants will undergo accelerated iTBS to 3 brain regions: medial prefrontal cortex (mPFC) (experimental site), dorsolateral prefrontal cortex (DLPFC) (alternative experimental site), or primary sensory cortex (S1) (control site). Participants will complete symptom questionnaires, neurologic examination and cognitive assessments, and orthostatic vital signs recording before and after each brain stimulation session.
Objectives:	

Primary Objective: Aim 1: To determine whether iTBS to the medial prefrontal cortex (mPFC) produces more robust changes in frontal midline theta (FMT) EEG power in people with Parkinson's disease compared with stimulation at the dorsolateral prefrontal cortex (DLPFC) or the primary sensory cortex (S1). Aim 2: A. To evaluate FMT power correlations with burden of autonomic symptoms in Parkinson's

disease. B. To evaluate FMT power correlations with burden of depression symptoms in Parkinson's disease

Exploratory Objectives:

Aim 3: To evaluate the effect of iTBS on autonomic symptoms one day after, and 4 days after stimulation. Aim 4: To evaluate the effect of iTBS on depression symptoms one day after, and 4 days after stimulation.

Aim 5: To create a database of EEG and TMS data in people with PD for the purpose of future research into novel neurostimulation therapies for PD NMS

Outcome measures:

Primary Outcome Measures: Aim 1: Degree of change of frontal midline theta power on EEG after brain stimulation. Aim 2: Degree of association between autonomic symptoms and frontal midline theta EEG power; Degree of association between depression symptoms and frontal midline theta EEG power.

Exploratory Outcome measures: Aim 3: Change in SCOPA-AUT and OHQ from before to after iTBS; Aim 4: Change in BDI-II from before to after iTBS

Study Population:

Study population will be men and women of all demographic groups with Parkinson's disease age 50-90 years who do not have a diagnosis of severe dementia who reside in North Carolina.

Phase:

N/A (pilot study)

Description of

UNC Medical Center will be the only participating site.

Sites/Facilities Enrolling

Participants:

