There is a very low theoretical likelihood that stimulation of neuronal circuits can lead to epileptic discharges. To minimize this risk, we will exclude potential participants with personal history of epilepsy or risk factors for epilepsy. If abnormalities on EEG or a seizure is witnessed during the course of the study, a referral will be made to the UNC Department of Neurology for follow up, and/or the participant's treating neurologist will be notified. In the unlikely event that a seizure with loss of consciousness is witnessed during the course of the study, the participant will be instructed not to operate a motor vehicle until cleared by the Department of Motor Vehicles (DMV).

One of the scales that will be administered assess symptoms of depression (BDI-II questionnaire). Upon receiving this questionnaire, the research coordinator will check the scoring for this assessment. If the patient scored in the "severe" range (>28 points), the PI will be notified, and appropriate immediate referrals for care will be made per the patient's preference. The participant's treating neurologist or primary care physician will be immediately notified via a phone call. 911 will be called in the event that a participant is threatening to hurt themselves or others.

Hearing loss is a potential risk of TMS. This is a rare and moderate to severe risk. To protect against hearing loss, ear plugs are worn by the participant and by the technical operator during stimulation sessions.

There have been rare reports of mood episode switches in people with Bipolar disorder after iTBS (from depressed mood to mania or hypomania). This is a rare but potentially severe.

Other potential risks associated with participation in this study include:

- Scalp irritation due to application of the electroencephalogram electrodes to the scalp. This is infrequent and mild.
- Headache and dizziness are rare and mild
- Muscle tightness and twitching during stimulation are very common and mild

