5.5 STRATEGIES FOR RECRUITMENT AND RETENTION

Recruitment: Our sample for this study is 48 participants with Parkinson's disease age 50-90 years (See Sample Size Calculation). To recruit 48 participants, we will need to pre-screen 400 potential participants, and screen 90 potential participants, according to our experience in recruiting people with Parkinson's disease at our center. Participants will be recruited from among patients who are seen in neurology clinics at UNC for evaluation and treatment of idiopathic Parkinson's disease. A member of the research team will review data available in Epic for eligibility and recruitment, and flag patients who may qualify for the study. The treating neurologist will also be asked to consider potential participants' eligibility and ability to provide informed consent. Once potential participants have been identified, they will be asked in person, over telephone, and/or emailed by our research team to assess their interest in the study, and provide information about the research study. If the potential participant indicates they are interested, the study coordinator or research assistant will set up a time for the potential participant to have a screening research visit.

Retention: Retention strategies will include incentive payment upon completion of all study arms. Additionally, the research staff will call the participant at least 2 days prior to each study visit to remind them of the upcoming visit.

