6.2 MEASURES TO MINIMIZE BIAS: RANDOMIZATION AND BLINDING

To control for bias, we have decided on a prospective, controlled, triple crossover (three stimulation locations at separate study visits) study design. Participants will be blinded as to stimulation location, and each participant will experience stimulation at all locations. Each participant will have all rating scales performed by the same rater. Potential confounding factors, such as age, disease duration, cognitive function, and overall disease severity will be evaluated and controlled for, as indicated, in the final statistical models.

Stimulation order will be randomized and counter-balanced. Participants are assigned a study ID number and randomized upon signing the informed consent form. Subject ID will be entered into the randomization algorithm by the research assistant. A randomization table will be generated by a computerized script that randomizes and counterbalances by ID, generating an Excel spreadsheet. We will perform complete counterbalancing, there are 6 potential sequences (mPFC-DLPFC-S1, mPFC-S1-DLPFC, DLPFC-mPFC-S1, DLPFC-S1-mPFC, S1-mPFC-DLPFC, S1-DLPFC-mPFC) and a plan for 48 participants. Every effort will be made to completely counterbalance our sample. Thus effects of stimulation order will be minimized.

Treatment Assignment Procedures: Participants will receive stimulation to the medial prefrontal cortex, the dorsolateral prefrontal cortex, and the primary sensory cortex. The order of stimulation will be randomized and counterbalanced. Randomization will be performed using a script that generates a

spreadsheet. Randomization will be done after the screening visit is completed, before initiation of stimulation sessions.

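### Counting each adverse event once per participant leaves recurrences after later sessions out of the event count in a three-session crossover

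*Combined protocol and SAP*

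**What the plan says.** The Synopsis (1.1) describes the design: "This is a randomized, single-blinded, triple crossover study with 3 one-day iTBS". Section 6.2 adds that "each participant will experience stimulation at all locations".

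On collection, section 8.3.5 says "All AEs will be captured and recorded at each stimulation visit in person", followed by telephone contacts on days 1 and 4. The adverse event log carries a date for each entry, and section 8.3.4 asks for the onset and duration of each episode of an intermittent event.

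On analysis, section 9.4.4 names two safety outcomes. One is a side-effect questionnaire completed at the end of each session and summarised by mean, median and range. The other is the presence of adverse events judged related to stimulation. For adverse events the counting rule is "Each AE will be counted only once per participant". The rule names neither session nor stimulation site, and the section specifies no adverse event table by session or site. Section 9.4.8 rules out listings of individual participants.

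**The concern.** The counting unit is the participant, but each participant is exposed three times, at three different sites. Under the sentence as it stands, someone with a headache after all three sessions contributes the same count as someone with one headache after one session.

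The three sites are the study's treatments, so a safety comparison between them needs the number of sessions at each site that were followed by the event. Counts limited to one per participant cannot supply that. Any site tabulation built from them would be too low at every site and would tend to shrink the differences. With no participant listings, a reader of the results would have nowhere else to see the recurrences.

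**Working it through.** The plan states no adverse event rate, count or precision for safety, so there is no figure of its own to reproduce. The calculation below is an illustration under stated assumptions.

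**Inputs from the documents**
- Participants: "Our sample for this study is 48 participants" (section 5.5).
- Sessions: 3 per participant, so at most 3 × 48 = 144.
- Orders: "there are 6 potential sequences" (section 6.2), so 48 / 6 = 8 participants per order if fully balanced.

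**Assumptions, not in the documents**
- The chance p that a given event follows a session is equal across sessions and runs from 0.02 to 0.90. Section 2.3.1 describes frequency only in words: "Muscle tightness and twitching during stimulation are very common and mild", with headache and dizziness called rare.
- Sessions are independent in the first calculation and correlated in the second.

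**1. Independent sessions, equal risk**

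Event-sessions expected = 144p. Counted under the rule = 48 × [1 − (1 − p)³]. Share lost = 1 − [1 − (1 − p)³] / (3p). Apparent incidence per session or site = counted / 144.

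| p | Event-sessions | Counted | Share lost | Apparent incidence |
|---|---|---|---|---|
| 0.02 | 2.9 | 2.8 | 2% | 0.020 |
| 0.10 | 14.4 | 13.0 | 10% | 0.090 |
| 0.30 | 43.2 | 31.5 | 27% | 0.219 |
| 0.50 | 72.0 | 42.0 | 42% | 0.292 |
| 0.90 | 129.6 | 48.0 | 63% | 0.333 |

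Worked line for p = 0.30: 1 − 0.7³ = 0.657; 48 × 0.657 = 31.5; 144 × 0.30 = 43.2; 1 − 0.657 / 0.90 = 0.27.

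**2. Positive correlation within a participant**

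A beta-binomial model was used with intraclass correlation ρ, a = p(1 − ρ)/ρ and b = (1 − p)(1 − ρ)/ρ. The chance of no event in three sessions is the product of (b + i)/(a + b + i) for i = 0, 1, 2. At p = 0.10 and ρ = 0.3, a = 0.233 and b = 2.1, so this is 0.900 × 0.930 × 0.946 = 0.792. The counted rate is 0.208 per participant against 0.300 event-sessions, a loss of 30.6%. At ρ = 0.6 the loss is 47.5%. If exactly the same people react every time, the count is p against 3p, so the loss is two thirds at any p.

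**3. Unequal sites**

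Assume risks of 0.50, 0.30 and 0.20 for mPFC, DLPFC and S1, with independent sessions, the six orders in equal numbers, and each event credited to the session where it first occurred.
- mPFC: (2 × 0.50 + 0.50 × 0.70 + 0.50 × 0.80 + 2 × 0.50 × 0.70 × 0.80) / 6 = 2.31 / 6 = 0.385.
- DLPFC: (2 × 0.30 + 0.30 × 0.50 + 0.30 × 0.80 + 2 × 0.30 × 0.50 × 0.80) / 6 = 1.23 / 6 = 0.205.
- S1: (2 × 0.20 + 0.20 × 0.50 + 0.20 × 0.70 + 2 × 0.20 × 0.50 × 0.70) / 6 = 0.78 / 6 = 0.130.

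The mPFC minus S1 difference falls from 0.30 to 0.255.

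**4. What does not change**

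The proportion of participants with at least one event in case 3 is 1 − 0.50 × 0.70 × 0.80 = 0.72. The counted rates also sum to 0.385 + 0.205 + 0.130 = 0.72.

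**The case against.** The strongest reply is that the sentence may mean something else. It comes straight after the statement that events are collected at the visit and on days 1 and 4, so it may only prevent one event from being counted at several contacts. The next sentence reports start date, stop date and duration for each event; on that view, headaches three weeks apart are separate events and nothing is lost. This reading is possible. It is not what the words say, because the stated limit is per participant. The date fields also cut the other way: if a recurrent event is counted once, the plan does not say which occurrence's dates and severity are reported.

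Second, the largest losses belong to very common effects such as twitching, which the questionnaire captures at every session without this rule. That stands in part. The questionnaire is completed at the end of the session, so it does not cover events reported on days 1 and 4, and no summary by site is stated. For effects the protocol calls rare, the loss is small if sessions are independent.

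Three stronger inferences are tempting, and the documents do not support them:
- **The rule understates harm generally, or is invalid in a crossover.** Participant-level incidence is a legitimate measure in any design and is unchanged here. The gap is the missing session unit.
- **Repeat events are discarded.** They remain in a dated log, the PI reviews events in real time (10.1.7), and the study team and advisors review all of them at least quarterly (9.4.6). Only the summary count is affected.
- **Later sessions will be reported as safer.** At p = 0.30, first occurrences would run 0.30, 0.21 and 0.147 over sessions 1 to 3, but the plan specifies no table by session and no rule crediting events to the first site. Balanced orders would also leave sites of equal risk equal on average.

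Nor is a recurrence here a re-exposure to the same site, since each session uses a different one.

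**Conclusion.** The point holds for event counts. On its plain wording the rule omits recurrences after later sessions, so event totals are understated, any incidence by session or site derived from them would be too, and site contrasts would be blurred.

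The size cannot be fixed from the documents. Across the assumed range, with independent sessions and equal risk, the loss runs from negligible for rare effects to more than half for very common ones; within-person correlation raises it towards the two-thirds ceiling. If the sentence was meant only to stop duplicate reports across contacts, nothing is lost, but the text should then say so. The change is worth making because one revised sentence settles both readings with data already collected.

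**What to change.** Replace the counting sentence in section 9.4.4 with:

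> Each AE term will be counted at most once per participant per stimulation session, attributed to the most recent session by onset date. One event re-reported at the visit, day 1 and day 4 contacts, or persisting into the next session without worsening, is counted once, under the session of onset. Events with onset before the first session are reported separately. Participants with at least one event, and the number of events, will be tabulated by stimulation site and overall.

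The separate line for events before the first session is needed because section 8.3.4 records events from consent onwards. The cost is the replaced text and slightly more tabulation; the dated log already allows each event to be assigned to a session.
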